13.7 Associated with Isokinetic Muscle Strength Testing

Participants may experience mild discomfort including risk of fall, dizziness, muscle strain, stretching, or mild fatigue. Participants may also experience bruising from pushing against a padded bar, skin irritation (including reddening and itchiness) from the straps, and general joint discomfort from isolating the knee joint.

Subjects will be informed of this possibility as well as their option to take rest periods and/or discontinue isokinetic muscle strength testing at any time during the evaluation. All participants will be given a warm-up period. The bar and straps will be positioned as comfortably as possible for each participant.

13.8 Associated with Motion Capture

There is a small risk of skin irritation from the tape used to attach the reflective markers. The tasks performed during motion capture are activities of daily living and therefore would place the participants at minimal risk for additional injury.

If skin irritation occurs, they will be instructed to apply over-the-counter anti-inflammatory creams, ointment or spray of their choice to the skin. In addition, to avoid injury subjects will be coached to take rest periods if needed and/or discontinue motion at any time during the evaluation.

13.9 Associated with Functional Performance Testing

There is a small risk of general fatigue or discomfort, slight risk of fall, additional knee pain from performing the tests, muscle soreness, shortness of breath and dizziness. To mitigate this, the staff conducting the tests will assist with the procedures and apply protections.

13.10 Associated with Breach of Confidentiality

The subject's Private Health Information could be accidentally breached during the research process. Many system wide safety guards are in place to prevent this occurrence, including:

Subject de-Identification, Badge-access, locked offices; controlled access to research offices and documents, password protected work stations and password complexity enforced; state-of-the-art and promptly updated firewall to block external web traffic; end-to-end encryption on all connections, automatic email encryption system for all outbound (off TSC server) email, Electronically secure online questionnaire access.

13.11 Risk Analysis

The Study Team will perform regular review of cumulative adverse events and will modify mitigation strategy as necessary. Baseline risk analysis is shown in **Table 13.11** below. It is intended that risks with higher overall risk score will be subject to greater and more frequent scrutiny and discussion of mitigation. As the study progresses, modifications to this analysis will be fully document and retained.

Table 13.11 Risk Analysis

Risk	Likelihood of Occurrence 1= not likely 2= possible 3= very likely	Potential Impact on Subject Safety 1=little 2= moderate 3= severe	Detectability 1= high 2= moderate 3= low	Overall Risk Score (Hierarchy of assessment and follow-up) (3-9)
Associated with FIS Administration	2	3	2	7

Associated with Placebo Administration	1	1	3	5
Associated with MRI	2	1	1	4
Associated With PRO Questionnaires	2	1	1	4
Associated With Physical Exam	2	1	1	4
Associated With Blood Draw	2	2	1	5
Associated With Isokinetic Muscle Strength Testing	2	1	1	4
Associated with Functional Performance Testing	2	1	1	4
Associated With Motion Capture	2	1	1	4
Associated with Breach of Confidentiality	2	2	2	6

14.0 Stopping Rules/Termination of Study Enrollment

The triggering of stopping rules will result in prompt discontinuation of subject enrollment, subject dosing and notification of the Medical Monitor and IRBs. Although dosing and enrollment will cease, all subjects currently taking or have completed Study Medication treatment up until that point will be followed according to the protocol for the occurrence of adverse events. Efficacy follow-up will be continued only if, in the Principal Investigators judgment, efficacy follow-up would be clinically meaningful. Subject dosing and enrollment will be reconvened only when permission is granted by the IRB.

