	
 3. Vital signs; 4. Medical and surgical history; 5. Demographic information; 6. Details of injury; 7. Severity of injury; 8. Medications; 9. Physical exam with range of motion (ROM) of the target limb; 10. BMI; 11. Urine pregnancy test for Women of Child Bearing Potential (WOCBP); 12. Blood analysis; 13. Completion of augmented PROs, including: NRS, IKDC, Lysholm, TEGNER, WOMAC and SF-12; 14. A radiograph of the target knee will be performed to confirm the presence of Kellgren-Lawrence grade II-IV OA; 15. The patients' medical record will be reviewed, and the subject will be interviewed to determine if inclusion/exclusion criteria are met; 16. Randomization. 
Patients who have met all eligibility criteria will be assigned, 1:1 via block randomization, to one of the two blinded study groups.
 
Visit 2 (Baseline) (Within 3 months of Visit 1)
 
Some procedures performed in this visit may be performed in Visit 1 provided that Informed Consent has been signed.
 
 1. Urine pregnancy test for Women of Child Bearing Potential (WOCBP) 2. Quantitative MRI; 3. Kinematic movement; 4. Assessment of muscle strength, isokinetic dynamometry; 5. Functional performance testing.
--	---

	
After randomization is performed, a Study Team member will then inform the Vail Hospital pharmacist of the subject's assigned randomization code the study medication will be obtained. The subject will take the first dose of study medication at the clinic.
 
Subjects will be instructed to self-medicate for day 2 followed by 28 days off. They will be instructed to begin a second course of treatment for two consecutive days (days 31 and 32).
 
Subjects will be reminded at Visit 3 in-person and over the phone 2-4 days prior to the last dosing of study medication about their upcoming dosing. If applicable, they will also be reminded to withhold current medications as instructed by the PI.
 
A Medication Log recording medication administration will be provided to the subject with instructions to complete during the period of administration.

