10.8 Phone Calls

Subjects will be contacted by phone three times while they are taking study medication to remind them to take the next dose of drug and to capture any adverse events.

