If the event is felt by the Principal Investigator to be either a SADR or an adverse reaction, every effort will be made to identify the event as related to the Study Medication. Adverse events that are generally felt to be attributable to the Study Medication occur in close temporal relationship to the onset of dosing. A discussion of AEs that are common with the Study Medication is found in the **Section 13.0** of this document.

All adverse reactions and SADRs will be followed until resolution or the Investigator judges the experience to be chronic or stable.

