12.3 Reporting of Adverse Events

12.3.1 Function of the Medical Monitor and FDA

An Independent Medical Monitor will be selected to oversee study safety. A detailed medical Monitoring plan will be submitted to FDA upon appointment of this individual and before the first subject is treated. This individual is to be an appropriately certified physician experienced in monitoring clinical trials.

The Principal Investigator will be responsible for confirming the severity of all adverse events. All serious events will be reported to the Independent Medical Monitor within 24 hours of their disclosure to the Principal Investigator. The Medical Monitor will review data or events reported by the Study Team within 72 hours of disclosure to the Medical Monitor.

During this time, appropriate care will be given to the study subject. If managing adverse events requires unblinding to the any member of the Study Team, the appropriate team member will disclose the group identity to the necessary medical provider.

The IRB will be notified of unanticipated and serious adverse events within 5 business days of identification. This reporting may come from the Study Team, the Independent Medical Monitor, or both.

Investigator Sponsor will notify FDA in an IND safety report (Form 3500A), unexpected fatal or life threatening suspected adverse reactions where there is evidence to suggest a causal relationship between the Study Medication and the adverse event will be reported as a serious suspected adverse reaction. This will be reported to the FDA no later than 7 calendar days after the sponsor-investigator's initial receipt of the information about the event.

Other unexpected serious suspected adverse reactions, where there is evidence to suggest a causal relationship between the Study Medication and the adverse event, will be reported as a serious suspected adverse reaction. This will be reported to the FDA on FDA Form 3500A no later than 15 calendar days after the sponsor-investigator's initial receipt of the information.

The sponsor must identify all IND safety reports previously submitted to FDA concerning a similar suspected adverse reaction and must analyze the significance of the suspected adverse reaction in light of previous, similar reports or any other relevant information.

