14.1 Termination of Enrollment by the Principal Investigator

The Principal Investigator may terminate study enrollment at any time for any of the following reasons.

1. Any unexpected serious or life-threatening AE that cannot be determined to be unrelated to Study Medication;
2. It is determined that the protocol precipitates multiple subject non-compliance issues beyond reasonably missed follow-up.

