14.2 Termination of Enrollment by the Medical Monitor

The Medical Monitor may terminate enrollment due to the emergence of significant safety signals.

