22.2 Appendix B – Study Schemata

Visit Type	Screening	Baseline (4)	Emailed patient questionnaires	Safety Blood Draw	Phone Calls	Study Visit	Study Visit	Study Visit	Emailed patient questionnaires	Unscheduled
Clinic Visit Number	1	2		3		4	5	6		
Visit Date			Every 3 days for 6 wks after first dose of study drug and weekly for 6 wks thereafter	2 weeks after first dose of study drug	3 times after first dose of study drug	2 weeks after last dose of study drug	6 months after first dose of study drug	12 months from first dose of study drug	18 months after first dose of study drug	As needed for AEs/SAEs
Acceptable Visit Window		within 3 months of screening	± 1 day	± 2 days		± 10 days	± 4 weeks	± 4 weeks	± 4 weeks	N/A
Procedures & Assessments										
Informed Consent (1)	X									
Randomization (Placebo or Fisetin) (5)	X	X								
Medical/Surgical History & Demographics	X									
Physical Exam with Range of Motion of Study Knee	X					X	X	X		X
Vitals	X	X				X	X	X		X
BMI	X									
Record concomitant medications & supplements	X	X				X	X	X		X
Blood Draw (6)	X	X		X		X	X	X		X
Urine pregnancy test for WOCBP (2)	X	X								
PRO questionnaires			X			X	X	X	X	
Radiograph of Study Knee (3)	X									
Quantitative MRI		X					X	X		
Biomotion tests (functional performance, joint range of motion, muscle strength, video motion analysis)	X	X					X	X		
Dispense study drug		X								
Provide study drug diary		X								
Return study drug and diary						X				
Review and Assess AEs and SAEs				X	X	X	X	X		X

FOOTNOTES:

(1) Informed consent must be signed by the patient prior to ANY research-related procedures. The informed consent document can only be signed by the study PI and/or the treating clinician (MD/NP/PA) who is on the protocol.
(2) WOCBP = Women of Child Bearing Potential
(3) To confirm the presence of Kellgren-Lawrence grade II-IV OA.
(4) Procedures at Baseline may be performed at the Screening Visit after the Informed Consent Form (ICF) is signed.
(5) Randomization can occur at Screening or Baseline as long as the ICF has been signed and patient eligibility in the study is confirmed.
(6) If the Baseline visit occurs greater than 3 months after the Screening Visit, blood should be collected again for safety purposes.

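### Section 14.0 makes the stop of enrollment and dosing mandatory, but no event listed in the protocol obliges the site to hold other subjects' self-administered second course

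*Combined protocol and SAP*

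**What the plan says.** Section 14.0 sets the consequence of a trigger: "The triggering of stopping rules will result in prompt discontinuation of subject enrollment, subject dosing and notification of the Medical Monitor and IRBs". It adds that dosing and enrollment restart only with IRB permission.

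The criteria follow in two subsections:

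- **14.1:** the Principal Investigator "may terminate study enrollment at any time for any of the following reasons". The first reason is an unexpected serious or life-threatening adverse event that cannot be ruled unrelated to Study Medication. The second is widespread non-compliance caused by the protocol.
- **14.2:** "The Medical Monitor may terminate enrollment due to the emergence of significant safety signals". The signals are not defined.

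On drug supply, the schedule in Appendix B (22.2) marks "Dispense study drug" at Baseline only. The Synopsis and 10.1 have subjects take days 31 and 32 on their own.

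Several safeguards exist. Appendix B places a blood draw and adverse event review at Visit 3, before the second course. Section 10.8 provides phone calls "to remind them to take the next dose of drug and to capture any adverse events". The Synopsis adds a reminder call 2 to 4 days before the last dosing, and 13.11 promises regular review of cumulative adverse events. Under 12.3.1, serious events go to the Independent Medical Monitor within 24 hours of disclosure to the Principal Investigator, and the Monitor reviews within 72 hours of being told. The same section says of the monitoring plan: "A detailed medical Monitoring plan will be submitted to FDA upon appointment of this individual and before the first subject is treated".

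**The concern.** Section 14.0 uses *will*; the only criteria that could set it off use *may* and speak of enrollment. A site following the text after a qualifying event could lawfully leave dosing untouched while the event is reviewed.

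That matters because of how the second course is supplied. The capsules are already in subjects' hands, so someone has to tell those subjects not to take them. None of the safeguards gives that instruction. The phone calls serve partly to prompt the next dose, and the care required by 12.3.1 during review is for the affected subject, not for others about to be re-exposed.

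Safety is the primary endpoint (8.2.1). A reader of 14.0 would believe that re-exposure stops automatically, when the protocol leaves it to judgment.

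**Working it through.** **Text check**

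| Section | Force | Covers | Event named |
|---|---|---|---|
| 14.0 | *will* | enrollment and dosing | none; refers to stopping rules |
| 14.1, reason 1 | *may* | enrollment | unexpected serious or life-threatening event, not ruled unrelated |
| 14.1, reason 2 | *may* | enrollment | multiple non-compliance issues, no count |
| 14.2 | *may* | enrollment | significant safety signals, undefined |

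No row combines a named event, an obligation and dosing.

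**Inputs**

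- Sample size: 72 (36 per arm, Section 6.0) to 100 (the maximum in 7.5.1 and 15.6). The plan states no count of subjects between courses, so there is none to reproduce. The 30 per group behind the 36 does reproduce by the normal approximation: 2 × (1.96 + 0.8416)² / 0.73² = 29.5, rounded up to 30; then 30 + 6 = 36.
- Enrollment: about 18 months (7.5.2). Even accrual is an assumption. A month is taken as 30.44 days.
- Gap between courses: 28 days (7.4.1).
- Longest review under 12.3.1: 24 h + 72 h = 96 h = 4 days from disclosure to the Principal Investigator.

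**Subjects between courses** = (N / months) × 28 / 30.44

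- N = 72: 4.00 × 28 / 30.44 = 3.68
- N = 100: 5.56 × 28 / 30.44 = 5.11
- On fisetin (half): 1.84 to 2.56
- Accrual over 24 months with N = 72: 3.00 × 28 / 30.44 = 2.76. Over 12 months with N = 100: 8.33 × 28 / 30.44 = 7.67.

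**Subjects reaching day 31 during the review** = (N / months) × 4 / 30.44

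- N = 72: 4.00 × 4 / 30.44 = 0.53
- N = 100: 5.56 × 4 / 30.44 = 0.73
- On fisetin: 0.26 to 0.37

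**Chance of at least one** (Poisson, 1 − e^(−mean))

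- Either arm: 1 − e^(−0.53) = 41%; 1 − e^(−0.73) = 52%
- Fisetin: 1 − e^(−0.26) = 23%; 1 − e^(−0.37) = 31%

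**How often a binding hold might be set off by coincidence**

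Take a trigger window from first dose to Visit 4: day 32 + 14 = day 46 (window day 36 to 56).

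- Person-years in the window: 72 × 46 / 365.25 = 9.1; 100 × 46 / 365.25 = 12.6.
- Assume 3 to 10 drug-unrelated unexpected serious events per 100 person-years (not in the documents): 9.1 × 0.03 = 0.27 to 12.6 × 0.10 = 1.26 events over the trial.
- Without a window, counting 12-month follow-up that falls inside the 18 months of enrollment: N / 1.5 × (0.5 + 0.5) = 48.0 to 66.7 person-years, so 1.44 to 6.67 events.

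Both ranges are upper bounds, since events determined to be unrelated would not count.

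**The case against.** The best defense is that 14.1 and 14.2 say who may act and 14.0 fixes what follows. On that reading a stop under either subsection carries dosing with it. Discretion is a defensible choice in a single-site Phase 1-2 trial, and an independent physician sees every serious event within days. Section 14.3 also lets the Principal Investigator remove a subject whose safety is at risk, and the reminder call shortly before the last dosing is a natural moment to say wait. Section 5.4 reports no serious events among 36 people treated under the referenced IND.

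Much of this stands, and it rules out stronger readings that a reader might infer:

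- *That the protocol names no triggering event.* It names one in 14.1; that event simply carries no obligation.
- *That dosing could never be stopped.* Section 14.0 can be read to cover it.
- *That serious events go without prompt independent review.* Section 12.3.1 provides it.
- *That everyone between courses is exposed because of the review interval.* The 3.7 to 5.1 are those holding capsules; only 0.53 to 0.73 come due within four days.
- *That no binding trigger exists anywhere.* The monitoring plan is outside the documents and might contain one, although 12.3.1 does not say so and Section 14 does not cite it.

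What the defense does not supply is an instruction to hold other subjects' doses while the review runs. The earlier experience reassures little about a second course: only four of the 36 had the two-month schedule, and zero events in four is compatible with a rate up to 1 − 0.05^(1/4) = 53% (one-sided 95% bound).

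**Conclusion.** The point holds as a gap between mandatory and permissive wording. No event in the protocol text obliges the site to hold pending second courses, although 14.0 reads as if a stop were automatic. The practical exposure is modest: under even accrual over 18 months and the longest review that 12.3.1 allows, about an even chance or somewhat less (41% to 52%) that one or more subjects reach day 31 before the review ends, and roughly half that for a subject on fisetin. Faster or slower accrual moves these figures in proportion.

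This is a worthwhile, inexpensive improvement to safety conduct. It does not show that oversight is absent, nor that every such event should halt the trial until the IRB agrees; with any hospitalization counted as serious (12.2.6), that would be debatable. Confidence about the wording is high. Confidence that the gap exists in practice is lower, because the monitoring plan cannot be seen.

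**What to change.** 1. In 14.1, state that a reason 1 event *will* pause new dosing and pending second courses until the Medical Monitor has reviewed it. Limit this to onset from first dose through Visit 4, plus later events judged a suspected adverse drug reaction or adverse reaction. The window fits the protocol's own view in 12.2.3: "Adverse events that are generally felt to be attributable to the Study Medication occur in close temporal relationship to the onset of dosing".
2. Require same-day calls telling subjects between courses to hold their capsules.
3. State that the full 14.0 stop, with restart only on IRB permission, follows if the Medical Monitor or the Principal Investigator does not clear the event.
4. State that stops under 14.1 and 14.2 cover dosing as well as enrollment. The second reason in 14.1, and 14.2, can stay discretionary.
5. If the medical monitoring plan already sets such triggers, cite it in 14.0.

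**Cost.** A few sentences and about four or five calls per pause (three to eight if accrual takes 12 to 24 months). A few second courses would slip past day 31 by some days. Visit 4 is timed from the last dose and moves with them; Visits 5 and 6 stay timed from the first dose but have four-week windows. There would be an occasional short pause for a coincidental event, about one at most over the trial under the assumed rates.

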14.1 Termination of Enrollment by the Principal Investigator

The Principal Investigator may terminate study enrollment at any time for any of the following reasons.

1. Any unexpected serious or life-threatening AE that cannot be determined to be unrelated to Study Medication;
2. It is determined that the protocol precipitates multiple subject non-compliance issues beyond reasonably missed follow-up.

14.2 Termination of Enrollment by the Medical Monitor

The Medical Monitor may terminate enrollment due to the emergence of significant safety signals.

14.3 Removal of Subjects from the Study

Principal Investigators may remove a subject from the study if:

1. A subject demonstrates poor compliance with study protocol;
2. There is concurrent illness or required medical treatment that interferes with study assessments;
3. The Principal Investigator determines that the subject's health, safety or welfare is at risk.

14.4 Withdrawal of Consent

Subject may withdraw their consent to participate in the Study at any time, for any reason.

15.0 Statistical Considerations

15.1 Study Overview, Aims and Objectives

The aim of this study is to perform a single-center randomized clinical trial (RCT) to test whether the dietary supplement Fisetin (FIS) can improve symptoms, kinematic function and soft tissue quality in patients with knee osteoarthritis. The proposed therapeutic systemic mechanism of FIS in this population is by selectively killing senescent cells that have been shown to associate with aging and age-related disease, including osteoarthritis (OA).

Assessments occur over 18 months following enrollment, and include safety monitoring, biomarker assessment, kinematic testing, quantitative MRI, knee-related patient reported outcomes, and observation of conversion to alternative treatment modalities. We hypothesize that the FIS treated group will not experience adverse events at a higher rate than the placebo group. Additionally, we hypothesize that improved OA disease status will be observed among the several pain, function and tissue quality endpoints for the FIS group when compared to the placebo group.

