15.5 Endpoints

15.5.1 Primary Endpoint

The safety of FIS administration is the primary endpoint of this study. All adverse events will be compared by category of description incidence, relatedness to treatment, severity, duration and expectedness. The occurrence of non-serious and serious and unexpected adverse events will be compared between treatment groups. Bivariate analysis will be performed between group and each safety variable of interest independently. When comparing the two treatment groups, dichotomous (yes/no) endpoints will be assessed for association using Fisher's exact test. Adverse events and symptoms that may occur multiple times in a single subject will be analyzed as count variables, and group differences will be assessed using simple Poisson regression or simple negative binomial regression.

This is a small Phase I/II trial in which to assess safety, thus we will report all safety data thoroughly and aim to liberally identify potential side-effects and risks that may warrant close study in future, larger trials. No adjustments will be made for multiple comparisons in this set of safety endpoints.

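### The safety hypothesis is that fisetin does not raise the AE rate, but the planned tests of no difference cannot support it and no confidence bound is tied to it

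*Combined protocol and SAP*

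**What the plan says.** Safety is the primary objective (8.1.1), and the occurrence of adverse events is the primary endpoint (8.2.1). Section 15.5.1 repeats this: "The safety of FIS administration is the primary endpoint of this study". The expectation attached to it is in 15.1: "We hypothesize that the FIS treated group will not experience adverse events at a higher rate than the placebo group".

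Section 15.5.1 names the methods. For yes/no outcomes, "dichotomous (yes/no) endpoints will be assessed for association using Fisher's exact test". For events that can recur in a subject, "group differences will be assessed using simple Poisson regression or simple negative binomial regression". The same section gives the purpose of the safety analysis, which is to "aim to liberally identify potential side-effects and risks that may warrant close study in future, larger trials", and adds: "No adjustments will be made for multiple comparisons in this set of safety endpoints".

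Section 15.4 has a general rule that inferential estimates are reported with confidence intervals. Neither 15.1, 15.4 nor 15.5.1 gives a margin, a largest acceptable excess, or a rule for judging the 15.1 hypothesis. The only sample-size calculation (15.6) concerns T1rho, a secondary endpoint. On size, section 6.0 gives 36 per arm. The synopsis gives a total of 100 and section 7.5.1 a ceiling of 100. Section 15.6 contains both the ceiling and 30 + 6 per group.

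**The concern.** The hypothesis is one of no excess. The named tests take no difference as their null, so they can produce evidence of an excess but not evidence that there is none. With a few dozen subjects per arm, a non-significant comparison is compatible both with no excess and with a clinically important one. The plan gives no other route from the data to the 15.1 statement.

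The 15.1 wording also sits poorly with 15.5.1. Liberal signal-finding without multiplicity adjustment is a reasonable aim for a Phase I/II trial, but it looks for harms and does not establish their absence.

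At stake is the wording of the trial's primary conclusion and what later trials take from it. Section 13.1 records positive Ames and micronucleus findings. Section 5.4 reports a transient creatinine rise in earlier work, judged possibly related to fisetin or placebo.

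**Working it through.** **Inputs.** Arm sizes are 36 (6.0, 15.6) and 50 (the ceiling of 100, allocated 1:1). No significance level is stated for the safety tests, so two-sided 0.05 is assumed, the level used in 15.6. The documents give no placebo AE rate, so every rate below is an assumption.

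**The plan's own figure.** For SMD 0.73, two-sided 0.05 and 80% power, n = 2(1.960 + 0.842)²/0.73² = 29.5, so 30 per group. This reproduces 15.6. The noncentral t gives power 0.794 at 30, which is close enough. Then 30 × 1.2 = 36. The calculation says nothing about AEs.

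**Fisher's test.** The probability of a non-significant result is the sum, over all pairs of counts with Fisher p ≥ 0.05, of Bin(x; n, placebo rate) × Bin(y; n, fisetin rate).

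| Assumed placebo v fisetin rate | 36 per arm | 50 per arm |
|---|---|---|
| 5% v 15% | 85% | 76% |
| 10% v 20% | 86% | 81% |
| 10% v 30% | 53% | 36% |
| 20% v 40% | 63% | 48% |
| 15% v 45% | 26% | 11% |
| 20% v 60% | 9% | 2% |

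At 36 per arm a tripling is more likely missed than found when the placebo rate is about 10% or lower. At 50 per arm that is so at 5% but no longer at 10%. From 15% upward a tripling is usually detected, and above 33% a proportion cannot triple. Power to detect a doubling at 36 per arm is 14% at a placebo rate of 10%, 37% at 20% and 64% at 30%.

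**Counts.** The standard error of the log rate ratio is √[(1/μ₀ + k)/n + (1/μ₁ + k)/n], where μ₀ and μ₁ are the mean AEs per subject and k is the dispersion. Power is Φ(ln RR/SE − 1.96). With an assumed μ₀ = 1, n = 36 and k from 0 to 1, power is 25–47% for a rate ratio of 1.5, 60–92% for 2, and at least 95% for 3. At n = 50 it is 32–60% for a rate ratio of 1.5.

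**What an interval would show.** The Newcombe interval combines the Wilson limits of each arm. For 4/36 in both arms, p = 0.1111 and the Wilson limits are 0.0441 and 0.2531. The half-width is √[(0.2531 − 0.1111)² + (0.1111 − 0.0441)²] = 0.157. Identical observed rates therefore still allow an excess of up to 15.7 points. The same method gives ±20.6 points for 11/36 in each arm, ±12.7 for 5/50 and ±17.5 for 15/50.

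**Zero events in an arm.** The one-sided 95% upper limit is 1 − 0.05^(1/n), which is 8.0% at n = 36 and 5.8% at n = 50.

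**One concrete table.** With 3/36 on placebo and 10/36 on fisetin, Fisher p = 0.063. The risk difference is 7/36 = 19.4 points, with a Newcombe interval of 1.4 to 36.6. The test alone would not flag this table, whereas the interval shows an excess that could be large.

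**The case against.** The strongest reply is that 15.5.1 describes signal-finding, for which tests of difference are the natural tool. The formal objective and endpoint in section 8 only evaluate safety, and the 15.1 sentence is an expectation in an overview with no decision attached. This stands in part. It means that the tests should stay, but it leaves the 15.1 hypothesis without a valid means of assessment.

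A reader might go further in three ways that the documents do not support.

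- That the plan offers nothing but significance tests. Section 15.4 requires confidence intervals for inferential estimates, and the count regression yields a rate ratio whose interval bears directly on whether the rate is higher. The gap is narrower. No absolute measure is named for yes/no AEs (the interval usually given with Fisher's test is for an odds ratio), and no bound is linked to the hypothesis.
- That p > 0.05 will be reported as confirming safety. No section says so, and the signal-finding sentence points the other way. The plan leaves that reading open but does not state it.
- That the AE rate could triple unnoticed. This depends on a placebo rate that the documents do not give. It is fair for infrequent AE types, but wrong for AEs at 20% or more on placebo, or for total counts near one per subject. Section 12.1 defines AEs broadly, so a low overall rate is doubtful.

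Nothing here shows a fault in the analysis set in 15.4, so the point gives no ground for changing it.

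**Conclusion.** The point holds as a mismatch between hypothesis and method for the primary endpoint. A non-significant Fisher test or count regression cannot support the 15.1 statement, and no interval bound or margin is in place to do so. That logic does not depend on any assumed rate.

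The size does depend on assumptions, namely the placebo rates, two-sided 0.05, and 36 or 50 per arm. Under these, a doubling from 10% or 20% is missed in about half to nearly nine in ten trials (48% to 86%). A tripling is likely to be missed only for AE types at about 10% or less on placebo. For common AEs the excess that may go undetected is nearer 1.5- to 2-fold.

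This should be fixed, but it does not invalidate the trial. Design, data collection and the planned tests are unaffected.

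**What to change.** In 15.1, replace the no-excess hypothesis with an estimation aim: to estimate the difference in AE risk and rate between fisetin and placebo, with its uncertainty.

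In 15.5.1, keep the planned tests and label them as signal-finding. Add:

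- for any AE, any SAE and each AE type, the fisetin-minus-placebo risk difference with a 95% Newcombe interval;
- for counts, the rate ratio with its 95% interval;
- for AE types with no events, the one-sided 95% upper limit;
- a statement that the safety conclusion is the size of excess that the upper limit excludes, and that p > 0.05 will not be described as 'not higher'.

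Leave the analysis set as the plan states it. Make the change before group labels are added to the data.

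The cost is a few sentences and one more column in the AE tables. The safety claim becomes more modest. Near the 5% boundary the Newcombe interval and Fisher's test can disagree, as in the 3 v 10 example, so the text should say that the interval carries the conclusion.
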